It is also one of the main causes of hospital stay and death in our country. The relevance of stroke is given by its mortality data, as well as the dependency of survivors. In the acute phase of stroke, mortality rises to 25% of cases, appearing more frequently in hemorrhagic strokes (up to 50% of deaths) than ischemic strokes (25%). Studies show that in the first six months after the circulatory event, many of these deaths are caused by cardiopulmonary complications; however, after this stage, significant clinical and functional stabilization is achieved. Of the total survivors, 30-40% will present some serious sequelae, up to 60% of users will present minor sequelae or no sequelae, and only 6% of cases with severe initial paralysis will completely recover mobility. These data demonstrate the importance of rehabilitation to facilitate the relearning of these patients, having been shown in previous studies to be useful in the user's recovery in terms of functional autonomy, also increasing the frequency of return home and reducing hospital stay. Similarly, a caregiver-mediated program has been shown to have the potential to improve bodily function, activity, and participation outcomes for these individuals with stroke.

In addition, caregivers participate more actively in the rehabilitation process, which can increase feelings of empowerment, reducing caregiver burden levels and easing the transition from hospital to home (4).

Generally, initial assistance in stroke begins with a call to the 061 or 112 services and arrival at the Emergency Department. Subsequently, the user is admitted to the Stroke Unit and once stabilized, they are transferred to the neurology ward. The importance of rehabilitation in the acute phase is given by the existence of a therapeutic window during which interventions can truly modify the course of the disease and achieve neuronal reactivation. This improvement may be due to the existence of an area of penumbra in the periphery of the ischemic zone, whose damage is potentially reversible, although it can only be achieved for a short and variable time of up to 24 hours if reperfusion of said tissue is achieved, as well as the resolution of diaschisis (transsynaptic failure of neurons connected to the damaged area). However, there is a brain reorganization that can be modulated by rehabilitation techniques through the phenomenon of neuronal plasticity, which determines the importance of an efficient interdisciplinary intervention (4, 5).

The role of the occupational therapist has its place at all levels of stroke intervention, both in direct action with the user, as well as in counseling and family or social support. Occupational intervention is initially directed at sensorimotor and perceptual-cognitive performance skills, as well as re-education and training in basic and instrumental activities of daily living (ADL); Subsequently, an intervention more oriented towards the social and labor integration of the person is proposed (6). Occupational Therapy (OT) intervenes on function, using specific procedures and activities to develop, maintain, improve and/or recover the performance of functions and activities necessary in daily life, compensate for dysfunctions and/or promote health and well-being. Based on the framework for occupational therapy practice, we classify this function into areas of occupation (basic and instrumental ADLs, rest and sleep, education, work, play, leisure, and social participation) and performance skills (motor skills and praxis, sensoryperceptual skills, emotional regulation skills, cognitive skills, and social and communication skills). Therefore, the initial objective of an intervention plan carried out from OT is to improve the user's independence in carrying out ADLs, achieving the highest possible level of autonomy and promoting their well-being and quality of life (6, 7).

According to a study published in 2015, the prognosis of stroke in Spain has changed in recent years. Both survival and functional outcome have improved as a result of the introduction of a new model of care. This new model, based on stroke units, early reperfusion therapies, physiotherapy and secondary prevention, has been promoted by the stroke strategy of the Spanish National Health Service in coordination with regional health authorities and healthcare professionals. health. However, this model does not take into account the intervention of OT in the discharge process, as other countries with positive results in functional independence do, among others (8).

Finally, it should be remembered that this pathology also has a relevant economic impact on the direct national health cost, plus those derived from its work and socio- family repercussions. According to a recently published study, the cost of patients admitted to stroke units in Spain is €27,711 per patient/year. More than two- thirds are social costs, mainly informal care (9).

Foundation

The early supported discharge (ESD) model for rehabilitation was introduced in the late 1990s and includes a well- resourced interdisciplinary team that coordinates discharge and plans, monitors, and continues rehabilitation in the hospital setting, home (10).

Based on randomized controlled trials conducted, there is evidence that early discharge with hospital follow-up (ESD) and with continued rehabilitation at home has beneficial effects in stroke users; However, the effects of the ESD service in routine clinical practice in Spain have not been investigated (11, 12). Likewise, there is a lack of published data regarding the impact of Occupational Therapy in the hospital discharge process along with conventional care and rehabilitation in terms of patient functional outcomes, caregiver burden, and health care costs. during the first six months after the stroke (13).

It is important to take into account the involvement of the family in the rehabilitation process, as well as their knowledge regarding the patient's illness and care to provide a stimulating and safe environment at home that reduces the risk of ulcers, muscle or tissue shortening. soft joints, dislocations, etc., in patients with sequelae motor deficit. The treatment provided in current public healthcare is insufficient, which may be worrying due to the limited recovery after stroke and the difficulty in community reintegration. This is why certain variables are of special interest when trying to assess the effectiveness of this type of action, such as motor improvement and the importance of functional mobility of the upper extremities, which can contribute to a better quality of life for patients. stroke survivors (13, 14).

There are at least three important perspectives to take into account in any project to assess actions on the consequences of stroke: the personal, the social and public health. From a personal perspective, returning home after a hospital stay for stroke and being able to participate in rehabilitation planning, as well as deciding goals, results in patient empowerment and greater satisfaction, improving mood and promoting well-being. From a social perspective, it helps the family feel less distressed when support is provided at home, it reduces the risk of readmission and stress-induced symptoms in family members, which is also an opportunity to improve the caregiver quality of life and reduce their risk of illness, as family members often report feeling a great burden as caregivers. From a public health perspective, making it safe to discharge with occupational therapy support means decreased costs. There are no studies in our environment that demonstrate whether discharge with OT support is effective and profitable, whether it increases the safety of patients and families, or whether patients perceive less anxiety and depression, higher levels of functional independence and a better quality of life. (5).

Research objectives

General Objective

The general objective of the present study is to determine if the early intervention of occupational therapy (OT) together with usual care in the hospital discharge process after stroke has a positive effect on the quality of functional independence of the patient, comparing it with the control group that will have the assistance regular care and rehabilitation.

We designed a four-week early OT intervention program for patients who have suffered a stroke with the aim of improving quality of life and facilitating their return home by providing them and their caregiver with knowledge about specific care and neurorehabilitation.

Specific Objectives

Primary outcome: Quality of life. Secondary results: Functional independence and support needs in activities of daily living, sensory-motor skills, perceptual-cognitive skills, communication skills, anxiety and depression levels.

Methods

Type and general design of the study

This is a prospective, randomized, controlled clinical trial. The population to be represented is that of patients who are discharged from the neurology service of the Virgen de la Victoria University Hospital (Malaga) and who, after medical discharge, are referred to the rehabilitation service of the Maritime Hospital of Torremolinos as outpatients by decision of the neurology and rehabilitation departments, but will not be inpatients in the Physical Medicine and Rehabilitation Unit for intensive rehabilitation.

Users who are referred to rehabilitation by obtaining a place as an inpatient, receive occupational therapy and physiotherapy daily for a period of maximum three months. However, patients who are referred to the rehabilitation service as an outpatient are taken home directly after discharge and are subsequently recalled for rehabilitation. The period that elapses from when they are discharged until they are called to begin their rehabilitation varies depending on the workload of the service, and can even be three months after discharge. Referral to external or intensive rehabilitation is made based on the rehabilitation potential, which takes into account certain criteria such as age, clinical situation and vascular injury existing at the time of discharge, social support, motivation and observed recovery. during admission. Patients assigned to the study program are included in an early occupational therapy intervention program and are compared with a control group that will receive usual care and rehabilitation.

Sample selection and size

The sample size "n" was calculated based on the main variable SAQOL-39 with the sample size determination formula for two independent groups, assuming a mean of 2.50, standard deviation of 0.75, significance level of 5%, a power of 80% and a critical difference of 0.54, obtaining a sample of 30 participants per group.

Therefore, two groups were formed: an intervention group of 30 patients who will receive the early Occupational Therapy program in addition to the rehabilitation that they would receive independently of this study, and a control group of 30 patients who will receive the conventional rehabilitation.

Eligible patients were assigned to EOTIPS or the control group according to a pre-established computer randomized designation in blocks of six.

Inclusion and exclusion criteria

All patients must have diagnostic confirmation of stroke with single or multiple vascular lesions that had occurred in the same time period, demonstrated by neuroimaging tests (CT or MRI), be over 18 years of age, go home on discharge and live within a maximum of 30 minutes away from the hospital center, with >2 or <26 points on the National Institute of Health scale (NIHSS), 30–100 points on the Barthel Index (BI) on the second day after the stroke (with BI 100, the patient

can be included if the Montreal Cognitive Assessment is <26) and having been referred to the rehabilitation service as an outpatient. Inclusion in the study occurs prior to hospital discharge, within a two- week interval after the stroke.

Exclusion criteria are: NIHSS > 26, BI < 30, and life expectancy < 1 year. Also excluded are people with a previous stroke, dementia or other types of diseases that cause dementia and other neurological, psychiatric or medical diseases (for example, severe epilepsy, traumatic brain injury, schizophrenia, COPD, severe or unstable heart disease, sleep apnea) concomitants that could alter cognitive function, presence of moderate or severe aphasia, people who do not understand Spanish or English, as well as patients who have been referred to the Physical Medicine and Rehabilitation Unit as inpatients to receive intensive rehabilitation or who are discharged to a care home.

The variables will take into account: age, sex, educational level, marital status, nationality, mother tongue, employment, vascular territory and lesion volume.

List of results and evaluations

Patient evaluations	
Quality of life	- SAQOL-39
Level of functional independence	- BI - mRS - SIS-16
Perceptual-cognitive skills	- MoCA
Sensory-motor skills	Fugl MeyerBergTime up & go
Communication skills	- CAL
Anxiety and/or depression levels	- Berg - Hamilton

Assessments to be used in the study (all translated into Spanish)

- Stroke and Aphasia Quality of Life Scale 39, SAQOL-39 (Lata-Caneda, Piñeiro- Temprano, García-Fraga, García- Armesto, Barrueco-Egido, Meijide-Failde, 2009). SAQOL-39 was derived from the Stroke-Specific Quality of Life Scale and four additional items specifically targeting patients with aphasia, covering four domains: physical, psychosocial, communication, and energy.
- Montreal Cognitive Assessment, MoCA (Lozano Gallego, Hernández Ferrándiz, Turró Garriga, Pericot Nierga, López- Pousa, Vilalta Franch, 2009). MoCA has been proposed as a screening tool that promises good sensitivity to deficits resulting from stroke and vascular cognitive impairment. MoCA includes sections on visuospatial/executive functions, naming, attention, language, abstraction,

memory, and orientation. It is scored out of 30 (extra point for <13 years of education) and the recommended "normal" limit is ≥26.

- *Modified Rankin Scale*, *mRS* (Van Swieten, Kodustaal, Visser, Schouten, Van Gijn, 1988). The mRS is used to describe disability in general. The scale ranges from 0 to 6, from perfect health with no symptoms to death.
- Fugl-Meyer sensory motor assessment, FMA (Ferrer González, Zarco Periñán, Ruiz de Vargas, Docobo Durantez, 2015). It evaluates the upper extremity (maximum score of 66 which corresponds to normal motor function) and lower extremity (maximum score of 34). Tenderness, passive range of motion, and pain during passive joint movements are also evaluated.
- Timed up and go, TUG (Hafsteinsdóttiret al, 2014). TUG assesses basic mobility, timing the time required for a person to stand up from a standardized chair, walk a distance of three meters, turn, return to the chair, and sit down again. A shorter time indicates better performance. It has been shown to be reliable and valid in this group of patients.
- Berg Balance Scale, BBS (Kudlac, Sabol, Kaiser, Kane, Phillips, 2019). BBS assesses functional balance. Performance on this test is scored from 0 (unable to perform) to 4 (normal performance) on 14 different tasks, including the ability to sit, stand, reach, bend, turn, and step. The maximum score on the BBS is 56. A higher score indicates better balance skills.
- Barthel Index, BI (Baztán, Pérez del Molino, Alarcón, San Cristobal, Izquierdo, Manzarbeitia, 1993). The Barthel Index measures the extent to which someone can function independently during basic activities of daily living (ADLs), i.e., feeding, bathing, grooming, dressing, bowel control, bladder control, grooming, chair transfers, ambulation and climbing stairs. Each performance element is rated on this scale with a given number of points assigned to each level. In this study, the modified version with 0–100 is used, where a lower score indicates dependence.
- Stroke Impact Scale 16, SIS-16 (Duncan, Lai, Bode, Perera, DeRosa, 2003). The usefulness of this scale is similar to that of the Barthel Index, although it is more sensitive than the latter for discriminating between patients with mild disabilities. It is designed especially for patients who have suffered a stroke, but it is also applicable to dementia. It is a reduced version of the Stroke Impact Scale version 3.0. The information can be obtained from the patient himself, or from the main caregiver (15) (16).
- Communicative Activity Log, CAL (Pulvermüller & Berthier, 2008). Scale that allows obtaining information on the communication capacity in the activities of daily life referring to comprehensive and expressive aspects of language. It is composed of 36 items (Likert-type scale, 0-6) that evaluate both the quality (items 1-18) and the quantity of patient communication (items 19-36). Performance is obtained through the sum of the scores on each item.

- Beck Depression Inventory, BDI-2 (Steer, Brown, 1996). It is a self-administered questionnaire that consists of 21 multiple-choice questions. It is one of the most commonly used instruments to measure the severity of depression.
- Hamilton Anxiety Scale (Lobo et al, 2002). This scale evaluates the severity of anxiety globally in patients who meet criteria for anxiety or depression. In addition, this instrument is useful to monitor the response to treatment. It is composed of 14 items, 13 referring to anxious signs and symptoms and the last one assessing the patient's behavior during the interview.

The evaluations were carried out in both groups (control and intervention group) before discharge (after completion of the informed consent) and three months after the neurological event.

Timeline and data collection

Hospital discharge planning

The rehabilitation and neurology departments were responsible for referring patients to the occupational therapist and including them in the study. Before starting rehabilitation, the occupational therapist and her family explored the patient's needs and desires and decide individual goals for the intervention period.

Occupational Therapy intervention during the discharge process. The intervention has a person-centered approach that is based on who the user is: their context, their history, their family members, their individual strengths and weaknesses. Individualized objectives will be established, taking into account the patient's potential and limitations. Examples of goals could be: being able to wash independently, hanging clothes or riding the bus, or how to manage bills. OT intervention may involve training in different activities or thinking about different ways to adapt to difficult situations to achieve a goal. For example, for some patients the intervention may consist of carrying out

ADLs in which they have a limitation with the support of the occupational therapist with the aim of enhancing their sense of security during its performance. Data will be collected through note taking and analyzed with qualitative content analysis.

The designed OT intervention includes:

- Prior to discharge: Initial evaluation and a hospital session.
- Post-discharge: A two-hour home visit, telephone follow-up, a one-hour visit one month after discharge and final evaluation three months later.

This early OT intervention will be carried out independently of the usual care of the rehabilitation service of the Torremolinos Maritime Hospital.

Time planning

The project will begin in January 2021 and was estimated to last one year and three months (estimated completion in March 2022). Finally, the project was completed on November 2022.

Day 1: Hospital (1 hour)					
Initial interview and evaluation.					
Day 2: Hospital (1 hour)					
Information about stroke. Postural care.					
Day 3: Home (2 hours)					
Environment assessment, equipment and					
recommendations and establishment of					
individualized objectives.					
Day 4 - day 29: PHONE FOLLOW-UP.					
Implementation of the rehabilitation by the patient					
and caregiver (individual objectives).					
Day 30: Home (1 hours).					
Final assessment of individualized objectives at					
home.					
After 3 months: Home (1 hour)					
Final evaluation.					

Results analysis plan

The following analysis model was followed: to study the differences that may exist between one group and another, before and after the intervention, a repeated measures ANOVA was carried out; to check how some variables influence others, a multivariate analysis was carried out and, finally, to know the mean and normal distribution of the variables, descriptive statistics were performed. An intragroup analysis was included by performing paired T-test studies along with Wilcolxon for non-parametric measurements. The program used for data analysis was JAMOVI (version 2.3.26).

Difficulties and limitations of the study

Regarding the limitations of this study, it is worth highlighting the biases possibly derived from the adherence to treatment of the users and their caregivers, as well as the behavior and involvement of the family member in the process that will likely induce differences in the results. It is worth highlighting the importance of the word of the patient and the caregiver due to the telephone process of the intervention, since it can lead to differences in the instructions provided by the occupational therapist and, therefore, in the treatment and final result.

Furthermore, an important limitation is the heterogeneity of the sample, since we are generally talking about patients who have had a stroke of any location, extent and volume. The random distribution of patients may result in the two groups having significant differences in the severity of their injuries or their potential for recovery. Also due to the heterogeneity of each patient's rehabilitation process, it is understood that, of the total sample size, certain patients will subsequently receive a greater number of conventional rehabilitation sessions than others, and some patients will probably not even receive any sessions. This is why it seems

interesting to subsequently study the care received by each user three months after discharge, as well as their level of functionality and quality of life.

Ethical considerations

During data collection, the anonymity of users was guaranteed. Participants will be informed of the intervention and will be asked to sign an informed consent, with participation being voluntary and allowing the user to abandon whenever they wish.

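### The stated 80% power is not tied to the planned SAQOL-39 test and includes no stated allowance for loss; a baseline-adjusted comparison is a nearly free improvement (minor)

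*Combined protocol and SAP*

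**What the plan says.** Under Sample selection and size, the combined protocol and SAP names SAQOL-39 as the main variable and uses "the sample size determination formula for two independent groups, assuming a mean of 2.50, standard deviation of 0.75", a 5% significance level, "a power of 80% and a critical difference of 0.54, obtaining a sample of 30 participants per group". The same section then forms "an intervention group of 30 patients who will receive the early Occupational Therapy program" and "a control group of 30 patients who will receive the conventional rehabilitation".

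The assessments are made "before discharge (after completion of the informed consent) and three months after the neurological event". Under Results analysis plan, group differences are studied as follows: "before and after the intervention, a repeated measures ANOVA was carried out". That section names no between-group estimate or confidence interval.

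No section gives an expected loss rate, an inflation of the sample, a replacement rule, the sidedness of the test, or the time point or type of measure (score or change) to which the mean, SD and difference belong. Under Ethical considerations, participants may withdraw at any time. Time planning records that "Finally, the project was completed on November 2022".

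**The concern.** The 80% is the plan's only statement of how sensitive the SAQOL-39 comparison is. Two things make it hard to use.

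- The number allocated equals the formula result, while the outcome is measured at three months. If that result assumed complete follow-up, each missed assessment lowers the power.
- The formula is for two independent groups at one measurement, but the planned test is a before-after repeated measures ANOVA, whose group-by-time term compares changes. The two match only if 0.75 and 0.54 are the SD and difference of a change.

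What is at stake is the reading of a null result. Without an estimate and interval, a reader would lean on an 80% that may not describe the test that was run.

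**Working it through.** **Inputs from the plan:** difference 0.54, SD 0.75 (standardised 0.54/0.75 = 0.72), 5% level, 80% power, 30 per group.

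**Assumed, because the plan is silent:** two-sided test; loss of 10% or 20% (27 or 24 per group assessed); correlation r between baseline and three-month SAQOL-39 of 0.3 to 0.7; normal scores; equal SDs at both times; no true baseline difference.

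**Step 1: reproduce the plan's figure.**
n = 2 × (1.960 + 0.842)² × (0.75/0.54)² = 30.28 per group. The stated 30 agrees within rounding. The t-test solution is 31.27. A one-sided 5% test gives 23.85, so 24.

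**Step 2: power by number assessed (two-sided, two-group comparison).**

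| Assessed per group | Normal formula | t-test (noncentral t) |
|---|---|---|
| 30 | 79.6% | 78.3% |
| 27 | 75.3% | 73.8% |
| 24 | 70.3% | 68.5% |

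The normal column belongs to the formula that yields 30. The t-test column is closer to what an analysis would deliver.

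**Step 3: the planned group-by-time test.** With two time points it is a two-group t-test on changes.

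- *Change reading:* 0.75 is already the SD of change, so the t-test column of step 2 applies.
- *Score reading:* SD of change = 0.75 × √(2(1 − r)). At r = 0.3 this is 0.887, and at r = 0.7 it is 0.581. Noncentral t power:

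| Assessed per group | r = 0.3 | 0.4 | 0.5 | 0.6 | 0.7 |
|---|---|---|---|---|---|
| 30 | 64% | 71% | 78% | 87% | 94% |
| 27 | 59% | 66% | 74% | 83% | 92% |
| 24 | 54% | 61% | 69% | 78% | 88% |

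On the score reading, 80% at 30 per group needs r of about 0.52.

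**Step 4: ANCOVA on the three-month score, adjusted for baseline.** With score SD σ, the variance term is σ²(1 − r²), against 2σ²(1 − r) for change. The ratio is (1 + r)/2, which is below 1 for any r below 1 and is the same under both readings. On the change reading, σ = 0.75/√(2(1 − r)). Power at 27 per group (ANCOVA simulated, 200,000 runs per cell; group-by-time from the noncentral t):

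| | r = 0.3 | 0.4 | 0.5 | 0.6 | 0.7 |
|---|---|---|---|---|---|
| Score reading, ANCOVA | 77% | 80% | 84% | 89% | 95% |
| Score reading, group-by-time | 59% | 66% | 74% | 83% | 92% |
| Change reading, ANCOVA | 89% | 87% | 84% | 82% | 79% |
| Change reading, group-by-time | 74% | 74% | 74% | 74% | 74% |

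ANCOVA is ahead in every cell, though it does not reach 80% in all of them. Repeat simulations differ by up to about one percentage point.

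**The case against.** **The number 30 is not wrong.** This stands. It reproduces within rounding, and by the plan's normal formula power at full follow-up misses 80% by only 0.4 points. A reader might infer a miscalculated or clearly underpowered trial; the documents do not support that.

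**The 30 might already contain an allowance.** A one-sided test needs 24 per group, and 24/0.8 = 30, which is exactly a 20% loss allowance. The general objective is worded directionally, in terms of a positive effect. A reader might therefore take an absence of margin as established; it is not, because it rests on an inferred two-sided test. The two-sided reading remains the more natural one: the plan mentions neither a one-sided test nor an allowance, and presents 30 as the direct result of the formula.

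**Loss may have been small.** Participants live within 30 minutes of the hospital, the final evaluation is at home, and those with "NIHSS > 26, BI < 30, and life expectancy < 1 year" are excluded. These features may limit loss, but they are not a stated allowance. The actual loss is unknown from the documents.

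**The planned test may have more than 80% power.** This also stands. The mean of 2.50 suggests a score, and on that reading power exceeds 80% at 30 per group once r is above about 0.52. A reader might infer that the repeated measures ANOVA must fall short; without r, that does not follow.

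**The study is complete, and repeated measures ANOVA is a valid analysis.** Both are true. Planning power now matters less than the estimate and its interval, which is why the main change below concerns the analysis. ANCOVA is a gain in precision and does not repair an invalid test.

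**Conclusion.** The point holds as a minor design and analysis matter. The plan gives no loss allowance and leaves sidedness and the meaning of 0.75 and 0.54 open, so its 80% cannot be tied to its planned group-by-time test. If the inputs describe change, that test has about 78% power with everyone assessed, falling to 74% or 69% with assumed losses of 10% or 20%. If they describe a single score, it has anywhere from 64% to 94% at 30 per group for r between 0.3 and 0.7, so the stated figure may be too high or too low. These figures assume a two-sided test, and r and the losses come from outside the plan.

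Taken alone, this is largely missing detail. It is worth acting on because the baseline SAQOL-39 already collected supports a more precise comparison at almost no cost: at 27 per group, about 77% to 95% power against 59% to 92% on the score reading, and about 79% to 89% against 74% on the change reading.

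**What to change.** Do not add patients.

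1. **Main change.** Compare three-month SAQOL-39 between groups by ANCOVA adjusted for the baseline score, and report the adjusted difference with its 95% confidence interval. Since the project is complete, label this as a post-completion change and report the repeated measures ANOVA beside it.

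2. **Supporting restatement.** State the sidedness, what 0.75 and 0.54 describe, whether 30 includes any allowance for loss, and how many were assessed. Name the test and formula to which any quoted power belongs. The two-group t-test figures should not be presented as the power of the ANCOVA, nor of the group-by-time test if the inputs describe a score. Do not compute power from the observed effect.

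Possible wording, to be completed by the sponsor:

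> *The sample size used a [one-/two-]sided 5% test. The SD of 0.75 and difference of 0.54 refer to [three-month score / change from baseline]. The 30 per group [included an allowance of x% / included no allowance] for loss; [n] and [n] were assessed at three months. Three-month SAQOL-39 is compared by ANCOVA adjusted for baseline, with the adjusted difference and 95% confidence interval. This analysis was added after completion; the repeated measures ANOVA is also reported.*

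The cost is a few sentences and one regression on data in hand. The downside is that an analysis chosen after completion must be disclosed as such.
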